**11.3.2 Skin lesion activity**

The assessment of skin lesion activity and skin lesion damage (Section 11.3.3) are based on the CLASI and RCLASI scoring scales for relevant disease signs (see Sections 11.2.6 and 11.2.7). The investigator will assess each target lesion for skin lesion activity at the visits indicated in the schedule of trial procedures (Section 4). The total skin disease activity score is defined as the sum of scores for erythema, scaling/hyperkeratosis, and oedema/infiltration.

**Erythema**

The investigator will score erythema for each target lesion on a 4-point scale:

0 = Absent.

1 = Pink, faint.

2 = Red.

3 = Dark red, purple/violaceous/crusted/haemorrhagic.

**Scaling/hyperkeratosis**

The investigator will give a combined score for scaling and hyperkeratosis for each target lesion on a 3-point scale:

0 = Absent.

1 = Circumscribed adherent scaling/follicular plugging.

2 = Verrucous hyperkeratosis.

### **Oedema/infiltration**

The investigator will give a combined score for oedema and infiltration for each target lesion on a 3-point scale:

0 = Absent.

1 = Slight, just palpable.

2 = Palpable and visible.

### **11.3.3 Skin lesion damage**

The assessment of skin lesion activity (Section 11.3.2) and skin lesion damage are based on the CLASI and RCLASI scoring scales for relevant disease signs. The investigator will assess each target lesion for skin lesion damage at the visits indicated in the schedule of trial procedures (Section 4). The total skin disease damage score is defined as the sum of scores for dyspigmentation and scarring/atrophy.

#### **Dyspigmentation**

The investigator will score dyspigmentation for each target lesion on a 4-point scale:

0 = Absent.

1a = Hypopigmentation.

1b = Hyperpigmentation.

2 = Hypo- and hyperpigmentation.

#### **Scarring/atrophy**

The investigator will give a combined score for scarring and atrophy for each target lesion on a 3-point scale:

0 = Absent.

1 = Initial scarring.

2 = Severe firm/atrophic/vermicular scarring.

## 11.4 Safety assessments

### 11.4.1 Vital signs

Vital signs (resting blood pressure, peripheral pulse, and body temperature) must be assessed according to the schedule of trial procedures (Section 4). Vital signs will be measured in a supine position following at least 5 minutes of rest.

If an abnormal vital sign at screening is considered clinically significant by the investigator, it will be at the discretion of the investigator if the subject should be randomised into the trial.

In case of abnormal findings, the vital sign measurement can be repeated approximately 15 minutes later with subjects resting in a supine position to verify the first measurement. Should the repeated measurement result in a normal value, the measurement must be repeated once more. If the third measurement verifies the second (normal) value, the first measurement should be considered false. If the third measurement confirms the first measurement (abnormal), the second measurement will be considered false. Only the last value measured and considered correct will be recorded in the eCRF.

#### Reporting in eCRF

Vital signs and the date and time they were measured will be recorded in the eCRF. If vital signs were not measured, a reason should be given. Clinically significant abnormal vital signs at the screening visit will be documented as medical history in the eCRF. At subsequent visits, any clinically significant deterioration of a pre-existing condition as well as any new clinically significant sign, symptom, or illness will be reported as an AE in accordance with Section 13.3.

### 11.4.2 Physical examination

A general physical examination of the subject must be performed according to the schedule of trial procedures (Section 4). This includes dermatologic examination of the skin, palpation of the abdominal organs, auscultation of heart, lungs, and abdomen, basic neurological status, and general examination of the eyes, ears, nose, and throat.

If an abnormal physical finding at screening is considered clinically significant by the investigator, it will be at the discretion of the investigator if the subject should be randomised into the trial.

### **Reporting in eCRF**

It will be recorded in the eCRF if a physical examination was performed and, if applicable, the investigator's evaluation ('normal', 'abnormal, not clinically significant', 'abnormal, clinically significant'); if a physical examination was not performed, a reason should be given.

Clinically significant abnormal findings at the screening visit will be documented as medical history in the eCRF. At subsequent visits, any clinically significant deterioration of a pre-existing condition as well as any new clinically significant sign, symptom, or illness will be reported as an AE in accordance with Section 13.3.

### **11.4.3 Electrocardiogram**

A single 12-lead resting digital ECG will be recorded after the subject has been supine for at least 5 minutes at the visit indicated in the schedule of trial procedures (Section 4).

A preliminary evaluation of the ECGs will be performed by the investigator to evaluate immediate subject safety. As a minimum, the date of ECG collection will be recorded in the source documents.

The ECG data will be transferred to a central ECG service company for central evaluation. A cardiologist at the ECG service company will analyse and interpret the ECG data. The ECG service company will provide ECG evaluation reports to the trial sites.

The investigator must evaluate all abnormal ECG results ('clinically significant' or 'not clinically significant') and sign and date. The investigator has the final decision on the clinical significance of ECG abnormalities.

If the screening ECG results in a finding, which is abnormal and of clinical significance, it will be at the investigator's discretion to decide if the subject should be randomised into the trial (respecting exclusion criterion no. 25).

The collection and transmission of ECG data will be described in a separate ECG manual. Test dummy transmissions will be undertaken prior to the trial conduct to ensure that transmissions can be made and that date and time settings are correctly set.

### **Reporting in eCRF**

It will be recorded in the eCRF if an ECG was performed and the investigator's assessment of ECG results ('normal', 'abnormal, not clinically significant', 'abnormal, clinically significant'); if an ECG was not performed, a reason must be given.

Clinically significant abnormal findings at the screening visit will be documented as medical history in the eCRF.

#### **11.4.4 Laboratory testing**

##### **11.4.4.1 Overview**

Blood and urine samples will be collected according to the schedule of trial procedures (Section 4).

The evaluations shown in Panel 10 will be performed.

**Panel 10: Clinical laboratory tests**

| Chemistry                         | Haematology  |
|-----------------------------------|--|
| Sodium                            | Erythrocytes   |
| Potassium                         | Haematocrit  |
| Creatinine                        | Haemoglobin  |
| Urea nitrogen                     | Erythrocyte mean corpuscular volume                    |
| Calcium                           | Erythrocyte mean corpuscular haemoglobin concentration |
| Alkaline phosphatase              | Leukocytes   |
| Aspartate aminotransferase        | Neutrophils  |
| Alanine aminotransferase          | Neutrophils/total cells                                |
| Gamma glutamyl transferase        | Lymphocytes  |
| Bilirubin a            | Lymphocytes/total cells                                |
| Lactate dehydrogenase             | Monocytes  |
| Cholesterol                       | Monocytes/total cells                                  |
| LDL cholesterol                   | Eosinophils  |
| HDL cholesterol                   | Eosinophils/total cells                                |
| Triglycerides                     | Basophils  |
| Haemoglobin A1c                   | Basophils/total cells                                  |
| Albumin                           | Thrombocytes   |
| Protein                           | Reticulocytes  |
| Urinalysis b           | Serology c                                  |
| Appearance                        | Hepatitis B virus surface antigen                      |
| Bilirubin                         | Hepatitis B virus surface antibody                     |
| Blood d                | Hepatitis B virus core antibody                        |
| Colour                            | Hepatitis C virus antibody                             |
| Glucose                           | HIV-1 antibody   |
| Ketones                           | HIV-2 antibody   |
| Leukocyte esterase d   | Antinuclear antibody                                   |
| Nitrite d              | Anti-DNA   |
| Protein d              | Anti-Smith antibody                                    |
| Specific gravity                  | Immunoglobulin G anticardiolipin antibody              |
| Urobilinogen                      | Immunoglobulin M anticardiolipin antibody              |
| pH                                | Lupus anticoagulant                                    |
| Urine pregnancy test e | Interferon gamma release test f             |
| Human chorionic gonadotropin      |  |

- a) If bilirubin is above ULN, direct and indirect bilirubin will also be measured.
- b) At screening, the urine sample will also be tested at the trial site with a urine dipstick to assess SLE-related renal disorder (see Section 11.2.5 and 11.4.4.2).
- c) Measured at screening only.
- d) In case of values outside the reference ranges, microscopic analysis will be performed.
- e) Only female subjects of childbearing potential. The urine pregnancy test will have a minimum sensitivity of 25 mIU/mL.
- f) Only subjects with high risk of latent tuberculosis.

**Abbreviations:** HDL = high density lipoprotein; HIV = human immunodeficiency virus; LDL = low density lipoprotein; ULN = upper limit of normal.

#### **11.4.4.2 Investigator evaluation of laboratory samples**

##### **Central laboratory**

Chemistry, haematology, urinalysis, and serology will be done by a central laboratory which will provide results to the trial sites. The investigator must evaluate all results outside the reference range ('clinically significant' or 'not clinically significant') and sign and date. The signed and dated version will be filed with the investigator's trial documentation. Clinically significant abnormal tests may be repeated if deemed relevant by the investigator.

If a screening laboratory result is abnormal and clinically significant, it will be at the investigator's discretion to decide if the subject should be randomised into the trial.

A laboratory manual will be provided to the trial sites specifying the procedures for collection, processing, storage, and shipment of samples, as well as laboratory contact information specific to this trial.

##### **Tests performed at the trial site**

Female subjects of childbearing potential will have a urine pregnancy test performed at the trial site at screening and at baseline prior to randomisation. The test will be repeated at the visits shown in the schedule of trial procedures (Section 4). The date and the outcome of the urine pregnancy test will be recorded in the eCRF ('positive', 'negative').

At screening, the urine samples will be tested for proteinuria with a urine dipstick to assess SLE-related renal disorder (ACR criterion no. 7, see Section 11.2.5 and Appendix 6). If the test is positive for proteinuria, the urine dipstick test must be repeated at least 1 week after the first test. If the second test is also positive, the subject is considered a screening failure due to violation of exclusion criterion no. 4. If the second urine dipstick test is negative, the subject can be included in the trial, as the observed proteinuria is then considered transient and not a sign of renal disorder as such.

##### **Reporting in eCRF**

At each visit, the site staff will record in the eCRF if a sample was taken and, if applicable, the date as well as the investigator's assessment of the results ('normal', 'abnormal, not clinically significant', 'abnormal, clinically significant'). If a sample was not taken, a reason will be provided.

Clinically significant abnormal laboratory results at the screening visit will be documented as medical history in the eCRF. At subsequent visits, any clinically significant deterioration of a

pre-existing condition as well as any new clinically significant sign, symptom, or illness will be reported as an AE in accordance with Section 13.3.

## **11.5 Pharmacodynamics and biomarkers**

### **11.5.1 Overview**

The pathogenesis of DLE is characterised by an inflammatory infiltrate localised in the dermis with presence of plasmacytoid dendritic cells and T cells. At the molecular level, the inflammatory response is dominated by type I and type II interferons and the chemokines CXCL9, CXCL10, and CXCL11, which are hallmarks of Th1 responses.

As an exploratory component of this trial, non-invasive skin samples and skin biopsies will be collected to create a general molecular profile of DLE and investigate how this profile changes upon treatment with delgocitinib. By comparing the expression of relevant biomarkers at the skin surface level (where drug exposure will be high) with changes across the whole skin depth in biopsies, it will be estimated to which extent the drug exposure in the dermis has been able to inhibit the pathogenic processes.

At all visits from baseline until end of treatment, non-invasive skin samples will be taken by applying a patch to the skin surface to absorb soluble material from the skin (see Section 11.5.2). After the trial, these patches will be analysed for disease-relevant cytokines and chemokines at the protein level. If no clinically relevant response to delgocitinib is seen, only patches from the baseline and end of treatment visits will be analysed.

Skin biopsies will be obtained at the end of treatment visit (Week 6) to analyse differences in gene expression (Section 11.5.3). Due to the invasive nature of this procedure, biopsies will be optional for the subjects. A focused panel of inflammatory and disease-related genes will be analysed by quantitative polymerase chain reaction (qPCR). A general expression analysis by microarray will be performed only if a clinically relevant response to delgocitinib is seen and if a sufficient number of biopsies is obtained to do a meaningful analysis.

Collection, handling, and shipment instructions for skin samples are provided in a separate laboratory manual. For subjects who do not complete the trial, the biopsies and non-invasive skin samples listed for Week 6 should be taken at the early termination visit.

A summary of the results will be included in the clinical trial report (CTR) if available at this time. The full results from the pharmacodynamics/biomarker analysis of all skin samples will be described separately in an addendum to the CTR.

### **11.5.2 Non-invasive skin sampling**

Non-invasive sampling of the skin will be done by applying a small patch to the selected skin area for 15 minutes. This will allow the patch to absorb soluble proteins that can diffuse through the skin. The patch will then be stored frozen in a vial until it will be analysed after the trial. Non-invasive skin sampling will not be done for subjects who have plaster or bandage allergy.

At baseline (prior to the first application of IMPs) and at the visits indicated in the schedule of trial procedures (Section 4), patches will be applied to each of the 2 target lesions. A representative area of each lesion should be selected. Another patch will be applied to a non-lesional skin location of similar anatomical origin. This procedure must be done prior to or at least 4 hours after IMP application.

It will be recorded in the eCRF if the samples were taken; if not, a comment should be provided. The non-lesional locations will be documented in the eCRF (scalp, forehead, temple, malar, cheek, eyebrow, lower eyelid, upper eyelid, lower lip, upper lip, chin, external ear, external nose, neck, trunk, arm, or leg).

### **11.5.3 Skin biopsies (optional)**

Subjects will be asked to provide skin biopsies. Participation in this component of the trial is optional and requires that the subject provides additional informed consent. Biopsies will not be taken if the investigator considers the procedure unsuitable for the subject (e.g. subjects receiving anticoagulant therapy).

3 skin punch biopsies (2 mm) for gene expression analysis will be taken at Week 6 or the early termination visit as specified in the schedule of trial procedures (Section 4). In case of an early termination visit, biopsies will only be taken if the subject has received treatment with the IMPs at least until the Week 2 visit.

Biopsies will be taken from each of the target lesions, and 1 biopsy will be taken from a non-lesional skin location of similar anatomical origin (same location used for non-invasive skin sampling at Week 6, see Section 11.5.2). Within each target lesion, the biopsy should be taken from a representative area of the lesion. For subjects who consent to having photographs taken, each target lesion should be photographed both before and after the biopsy to document the biopsy site.

The biopsies will be stored in tubes containing RNAlater at ambient temperature until the next day and then stored frozen until analysis.

For subjects who have provided consent to this part, it will be recorded in the eCRF if the biopsies were taken; if not, a comment should be provided. The non-lesional biopsy site will be documented in the eCRF.

A check of skin biopsy wound healing including removal of suture, if applicable, will be performed at the safety follow-up visit.

## **11.6 Other assessments**

### **11.6.1 Subject assessments**

#### **11.6.1.1 Patient's Global Assessment**

Subjects will assess the disease severity of each target lesion using the PaGA at the visits specified in the schedule of trial procedures (Section 4). The assessment will be made using the 5-point scale:

- 0 = Clear.
- 1 = Almost clear.
- 2 = Mild.
- 3 = Moderate.
- 4 = Severe.

The assessment will be based on the severity of the DLE lesions at the time of the assessment (and not in relation to the severity at previous visits). The PaGA should be completed before the investigator's assessments and without the investigator or site staff discussing the severity of the target lesions with the subject. The investigator will explain the categories of the scale to the subject who will then indicate which category should be ticked.

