### **9.3.1 Blinding**

The packaging and labelling of the IMPs will contain no evidence of their identity. However, there is a slight difference in colour between the 2 IMPs. The difference is only discernible on close inspection with both IMPs compared side by side. To avoid accidental investigator unblinding, the first application of IMPs and instructions to the subjects will only be done by designated trial site staff who are not involved in clinical evaluations.

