#### Panel 6: Sequence of assessments

- a) At the screening visit, the subject's eligibility to enter the trial must be confirmed before any subject assessments can be completed.
- b) Photographs of lesions (optional), non-invasive skin sampling, skin biopsies (optional).

Subjects participating in the trial will be under careful supervision of a principal investigator who must be a dermatologist. Investigators must be physicians who are experienced in treating DLE and have documented experience and/or training in use of the assessments

required by the protocol. In United States, the investigator can also be a certified physician's assistant or advanced registered nurse practitioner.

AEs must be assessed by medically qualified personnel (Section 13.2).

Whenever possible, the same investigator should perform all the evaluations for a given subject throughout the entire trial period to reduce inter-rater variability.

The investigator(s) performing the assessments must not be involved in the administration of IMPs (see Section 9.3.1).

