## **11.3 Efficacy assessments**

### **11.3.1 Investigator's Global Assessment**

The IGA is an instrument used in clinical trials to rate the severity of the subject's global disease and is based on a 5-point scale ranging from 0 (clear) to 4 (severe) (Panel 9). In this trial, the investigator will use the IGA as a lesion-specific assessment to rate the severity of DLE for each of the 2 target lesions.

The IGA score will be assessed according to the schedule of trial procedures (Section 4). The assessment will be based on the condition of the disease at the time of evaluation and not in relation to the condition at a previous visit.

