## 12.2 Appropriateness of assessments

The trial endpoints have been selected to evaluate the efficacy of delgocitinib in reducing the disease activity of DLE. The clinical efficacy of delgocitinib will be assessed using the IGA and specific disease activity scores from the CLASI and RCLASI.

There is no single, standardised grading system for disease severity in DLE. The IGA scale is a static, ordinal, 5-point scale used to rate the subjects' disease from 'clear' to 'severe' (see Section 11.3.1). The scale is defined by distinct and clinically relevant morphological descriptions to minimise inter-rater variation.

The 2 target lesions will be evaluated and scored separately. The IGA scale will allow for an overall qualitative assessment of the disease severity of the target lesions. The scale can be dichotomised to treatment success (score 0 or 1 at Week 6, that is, a  $\geq 2$ -point reduction in IGA score from baseline) and failure, representing a meaningful clinical outcome.

The CLASI and RCLASI have been developed and validated for assessment of disease severity in CLE patients. Both the CLASI and RCLASI score the activity and damage of the disease separately, considering both anatomical region and morphological aspects of skin lesions. In this trial, the skin lesion activity and damage signs scores are applied to the target lesions only. The individual sign scores and sum will give a quantitative assessment of the treatment effect. In addition, full CLASI and RCLASI assessments will be done at screening to describe the overall CLE disease burden in the trial population.

The PaGA is included to capture the subjects' perception of disease severity.

The safety of the IMP will be assessed by vital signs and clinical laboratory measurements and AE monitoring which will include local tolerability.

Skin biopsies (optional) and non-invasive skin samples will be taken for analysis of expression of inflammatory and disease-related genes and biomarkers to explore the molecular components of the disease and drug target engagement (see Section 11.5.1).

Exit interviews have been included as a recognised means of gaining better understanding of the patient experience of disease signs/symptoms and HRQoL impacts, and the IMP and trial procedures (30). Exit interviews are considered particularly valuable in a rare disease such as DLE where there is limited prior literature and knowledge about the patient experience.

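### Nothing keeps the subject's PaGA rating of each lesion from the investigator who then scores the IGA, the primary endpoint

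*Combined protocol and SAP*

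**What the plan says.** Section 11.6.1.1 sets two safeguards for the PaGA. One concerns order: "The PaGA should be completed before the investigator's assessments". The other bars both the investigator and site staff from talking with the subject about how severe the lesions are. The section then describes how the rating is taken: "The investigator will explain the categories of the scale to the subject who will then indicate which category should be ticked". It does not say who ticks the box, who is present, or who sees the completed form.

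On the primary endpoint, Section 11.3.1 states that "the investigator will use the IGA as a lesion-specific assessment to rate the severity of DLE for each of the 2 target lesions". Section 11.1, in the text after Panel 6, adds: "Whenever possible, the same investigator should perform all the evaluations for a given subject throughout the entire trial period to reduce inter-rater variability". The one separation of roles required there is that assessors take no part in administering the IMPs. Section 9.3.1 gives the reason: the two creams differ slightly in colour, and "The difference is only discernible on close inspection with both IMPs compared side by side".

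Section 12.2 explains the purpose of the scale: "The PaGA is included to capture the subjects' perception of disease severity". In Section 6 the PaGA endpoints are exploratory.

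**The concern.** The safeguards run in one direction. They protect the subject's rating from the investigator's opinion, but they do not protect the investigator's rating from the subject's. An assessor who knows that the subject has just called one lesion almost clear and the other mild may be anchored when placing the same two lesions on a scale with the same five labels.

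Two features of the design make this worth closing. First, the comparison is within subject, and McNemar's test uses only the pairs in which the two lesions differ. A cue about which lesion is better acts on exactly those pairs. Second, the subject keeps both creams at home and applies them twice daily for 6 weeks, so the subject can make the side-by-side comparison that Section 9.3.1 treats as the condition for seeing the colour difference. A subject's belief about allocation could reach the assessor through the PaGA, although the assessor is kept away from the creams.

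**Working it through.** **1. The relevant text, side by side.**

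| Question | What the protocol gives | Where |
|---|---|---|
| Who explains the PaGA? | The investigator | 11.6.1.1 |
| When is it completed? | Before the investigator's assessments; no interval given | 11.6.1.1 |
| Who records the answer? | Not stated; the subject indicates a category | 11.6.1.1 |
| Who scores the IGA? | The investigator, for each lesion | 11.3.1 |
| Same person throughout? | Yes, whenever possible | 11.1 |
| At which visits do both occur? | Screening, baseline, Weeks 2, 4, 6 and 8, and early termination | Panel 2 |
| Same grades? | Both 0-4: clear, almost clear, mild, moderate, severe | Panel 9; 11.6.1.1 |
| Is the PaGA hidden from the IGA assessor? | No provision found | 11.1, 11.3.1, 11.6.1.1 |

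The investigator is therefore present when the scale is explained, and the wording suggests that the subject's answer is given to someone. Exposure of the assessor is allowed and likely, but not stated. The Panel 6 figure is not shown in the text available, so the exact sequence and timing cannot be checked.

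**2. The plan's own figures.** Section 14.1 aims for 36 completers, with 5% success on vehicle, 35% on delgocitinib and at least 90% power. A normal-approximation calculation for two independent proportions with 36 lesions per treatment gives 0.906, and 36 / (1 - 0.20) = 45 randomised. Both agree with the plan. Neither depends on the PaGA.

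**3. What an effect could look like.** The documents give no size of influence, so this is an illustration only. Inputs from Section 14.1: n = 36 pairs and 5% success, applied here to both lesions independently (no drug effect). Assumed inputs: a share m of pairs in which the known rating turns one lesion into a success, and a share g of those in which that lesion is the active one.

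- P(active success only) = (1 - m) × 0.05 × 0.95 + m × g × 0.95
- P(vehicle success only) = (1 - m) × 0.05 × 0.95 + m × (1 - g) × 0.95
- Paired difference = 0.95 × m × (2g - 1)

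For m = 0.10 and g = 0.7 the two probabilities are 0.04275 + 0.0665 = 0.10925 and 0.04275 + 0.0285 = 0.07125, a difference of 0.038. Enumerating all outcomes for 36 pairs, the chance of a two-sided 5% result favouring delgocitinib is:

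| m | g | Difference (points) | Uncorrected McNemar | Exact McNemar |
|---|---|---|---|---|
| 0.10 | 0.5 | 0 | 2.3% | 0.7% |
| 0.10 | 0.7 | +3.8 | 6.9% | 2.7% |
| 0.10 | 0.8 | +5.7 | 11.1% | 4.9% |
| 0.20 | 0.7 | +7.6 | 12.2% | 7.6% |

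The nominal one-sided share is 2.5%. Section 14.3.4 names McNemar's test without saying which version, and the choice changes these figures considerably. With g = 0.5 there is no bias in either direction.

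**The case against.** The strongest reply is that the documents show an unspecified detail and not a demonstrated bias. Several parts of it stand.

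- **Timing and exposure.** A reader might infer that the assessor hears the rating moments before scoring. The text says only that the PaGA comes first, and it leaves open who ticks the form and who sees it. Exposure is a reasonable inference and should be put no more strongly than that.
- **Inflated false positives.** A reader might take the table above as an estimate. It is not. With no drug effect there is no efficacy clue, so only the colour difference could make guesses better than chance. Seeing that two creams differ does not show which one is active, and no passage says that the colour identifies delgocitinib. Nothing in the documents supports g above 0.5. If the drug does work, a subject who prefers the active lesion may simply be seeing real improvement.
- **Room for anchoring.** Panel 9 separates grade 1 from grade 2 by whether scaling or oedema is present, Section 12.2 says the descriptors are meant to limit inter-rater variation, and Appendix 3D requires assessor training. These reduce the scope for anchoring. They do not remove it, because deciding whether a slight sign is present is still a judgement.
- **Dependence of the two scales.** A reader might object that PaGA and IGA are not independent. They rate the same lesions and would correlate anyway, no analysis assumes independence, the PaGA is exploratory, and Section 14.3.11 reads every test descriptively and on its own. This is not a defect.
- **Other routes.** The investigator also asks an open adverse-event question at every visit (Section 13.2), so some opinion from the subject may reach the assessor in any case. That limits the benefit of a change, but a free remark is a weaker cue than a grade for each lesion on the assessor's own scale.

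The no-discussion rule does not answer the point: it limits what staff say to the subject and does not hide the subject's answer. Descriptive interpretation does not remove bias from an estimate.

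**Conclusion.** The point holds as a minor one. As written, Section 11.6.1.1 together with Sections 11.1 and 11.3.1 allows the primary assessor to know the subject's grade for each lesion before scoring the IGA, and no provision prevents it. This may anchor the primary endpoint and opens a possible way around the assessor separation in Section 9.3.1. Neither the size nor the direction of any effect can be derived from the documents. The differences of +3.8 to +7.6 points in the illustration rest on assumed values of m and g, and the false-positive figures depend also on the McNemar version. With random guesses neither treatment is favoured. The sample size and power statement are unaffected.

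**What to change.** Reword Section 11.6.1.1 on two points. First, the categories are explained by the investigator or any site staff before a rating is given, and the subject then ticks the form alone. Second, the completed form is neither shown nor told to the assessor until the IGA and the lesion activity and damage scores for that visit have been entered. Completing the PaGA before the investigator's assessments, and the no-discussion rule, both stay.

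The cost is one paragraph of protocol text, a line in site training and a small change in workflow at each visit with a PaGA. No non-assessing staff member is needed at every visit, and there is no new form, visit or procedure.
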